A.6. Depressive vs. Sickness Symptoms in Endotoxin Model: Low-dose endotoxin can induce not only depressive symptoms but also some sickness symptoms (i.e., lethargy, fatigue, muscle pain, headache, shivering, and nausea). Although in clinical practice depressed individuals experience both emotional and somatic symptoms of depression in varying degrees, a possible critique on the endotoxin model would be that depressed mood might be majorly influenced by sickness symptoms. To minimize this possibility, we have previously used a depression scale that only assesses emotional symptoms such as “unhappy”, “sad,” and “hopeless” (Profile of Mood Scale [POMS]⁶⁷).²¹⁻²³ Furthermore, we have used analytical procedures to ensure the effects of endotoxin on depressed mood are independent of sickness symptoms (Preliminary Data). In this study, beyond these two measures, we will use experimental tasks of negative and positive affect to assess mood-specific processes (see C.2.6. Experimental Tasks). This innovative approach is particularly important for this study as we hypothesize that leucine pretreatment—which interferes with the transport of excess KYN into brain without modifying inflammatory responses to endotoxin—will specifically abrogate depressed mood but not sickness symptoms induced by endotoxin. *This study is significant because it will examine depressive vs. sickness symptoms in a human endotoxin model of depression by employing mood-specific assessments and especially by testing a treatment that may act on a mood-specific mechanism without modifying inflammatory responses to endotoxin.*

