C.1.3. Endotoxin induces changes in KYN metabolism, which correlates with depressed mood

[figure not shown]

Fig. 5 Leucine reduces brain KYN:TRP ratios and blocks depression-like behavior. **A,B** Mean sucrose preference (%) and time spent immobile in the forced swim test (s) (\pm SEM) of mice treated with leucine or vehicle immediately before and 6 h after LPS or phosphate-buffered saline (PBS) ($n > 14$ per group). **C,D** Mean KYN:TRP ratios in plasma and brains (\pm 442 SEM) of mice treated with 50 mg/kg leucine or vehicle immediately before and 6 h after LPS or PBS ($n = 5$ per group).

** $p < 0.01$, *** $p < 0.001$ for LPS vs. PBS main effects. * $p < 0.05$, ** $p < 0.01$, *** $p < 0.001$ for leucine vs. vehicle main effects.

Aim: In the aforementioned study in C.1.2. (N=115), we examined whether endotoxin induces changes in kynurenine metabolism and whether these changes correlate with inflammation-induced depressed mood.

Methods: Circulating kynurenine metabolites (TRP, KYN, QA, KynA) were measured at T₀, T₂, and T₆. The primary outcome was IDO activity assessed using KYN/TRP. **Results:** Participants exposed to endotoxin (vs. placebo) showed greater increases in IDO activity (p<0.0001). Among endotoxin-exposed participants (N=61; 38 females), the correlation between IDO activity and depressed mood was highly significant (p=0.004).

Conclusion: Inflammatory challenge increased IDO activity, which in turn was significantly correlated with inflammation-induced depressed mood. *These data confirm endotoxin-induced increases in peripheral conversion of TRP to KYN as well as increases in depressed mood, and thus show the feasibility of inhibiting blood-to-brain transport of KYN as well as inflammation-induced depressed mood.*

C.2. Research Design and Methods

C.2.1. Overview of Study Design (Fig. 6):

In this double-blind randomized placebo-controlled four-arm study, a total of 90 healthy volunteers (ages 18-65) will be randomly assigned to a two-week pretreatment of L-leucine (hereafter referred to as leucine) or PO placebo (i.e., maltodextrin). After the pre-treatment period, they will receive low-dose endotoxin or IV placebo (i.e. saline): n₁=35 leucine + endotoxin; n₂=35 PO placebo + endotoxin; n₃=10 leucine + IV placebo; n₄=10 PO placebo + IV placebo. (see Justification of Sample Size for the rationale for smaller IV placebo arms)

[figure not shown]

Fig. 6 Overview of study design

C.2.2. Subjects:

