Pretreatment: Leucine is commercially available in US as dietary supplements. For this study, we will use oral preparation of the pharmaceutical grade leucine (12 g/day in 2 divided doses for 2 weeks; Ajinomoto, Raleigh, NC) mixed with effervescent powder. PO placebo will resemble the compounded mixture of leucine and effervescent powder. Clinical studies of leucine have used doses ranging from 2 to 18 g/day.⁸¹⁻⁸⁷ According to a meta-analysis, the long-term supplementation dose (i.e., 10 days to 6 months) ranged from 2.8 to 16.1 g/day with a weighted mean of 8.5 g/day.³⁰ Caspenson et al. found that leucine 12 g/day for 2 weeks improved muscle protein synthesis with a concomitant increase in phosphorylation of mechanistic target of rapamycin (mTOR) following the stimulus of a meal.⁸⁷ As this above-average dose given for 2 weeks caused increases in post-prandial protein synthesis and mTOR activation, both mechanisms also observed in preclinical studies of leucine after the stimulus of endotoxin,⁸⁸ we will use 12 g/day for 2 weeks. Participants will be given leucine or PO placebo on the day of in-person screening and will take it for 2 weeks including the morning of endotoxin administration, hence a total of 28 doses. At the end of pretreatment, subjects will indicate the presence or absence of a number of possible adverse effects in a questionnaire using a 4-point scale from 'not at all' to 'very often': symptoms include not feeling well, headache, weakness, fatigue, nausea, vomiting, burping, stomachache, bloating, flatulence, constipation, diarrhea, dry mouth, change of taste, cough, skin complaints, muscle pain, weight gain, weight loss, dizziness, sweating, and shaking. The adherence will be assessed using the Patient Adherence Questionnaire (PAQ)⁸⁹ and the count-back method (i.e., counting doses remaining in returned packets)⁹⁰ at the end of the pretreatment (i.e., immediately before endotoxin).

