Behavioral Measures: Depressed mood, a core symptom of depression, will be assessed immediately before endotoxin administration (T_0) and then hourly for the next 6 hours (T_1-T_6) using the POMS⁶⁷ (primary outcome). We will also use the MADRS⁹⁷ hourly (T_0-T_6) as it is sensitive to acute changes in depressed mood and anhedonia following endotoxin¹⁹ and is less oriented towards somatic symptoms than the Hamilton Depression Rating Scale. Because feelings of social disconnection and loneliness predict depression and co-occur with depressed mood following inflammatory challenge, feelings of social disconnection (Feelings of Social Disconnection Scale²¹) and loneliness (adapted UCLA Loneliness Scale⁹⁸) will also be assessed.

Participants will also complete self-report measures of sickness symptoms (e.g., muscle pain, fatigue).

Cognitive Measures: Three items from the POMS-Confusion subscale (unable to concentrate, forgetful, confused) will be assessed at T_0 and then hourly (T_1-T_6).⁶⁷ Verbal memory, visual memory, executive function, and attention be assessed at T_0 and then between T_2 and T_3 using computerized tests from CNS Vital Signs™: Verbal Memory Test, Visual Memory Test, Stroop Test, Shifting Attention Test, and Continuous Performance Test. Reichenberg et al. assessed cognitive impairment at 1, 3, and 9 hours after endotoxin and found it to be worst at 3 hours.²⁰ The order of tests will be counterbalanced across subjects to avoid any non-random version-dependent bias.⁹⁹

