Reward (Reward Learning Task): Anhedonia is a core feature of major depressive disorder and includes a reduction in experienced pleasure (liking reward) and dysfunction in reward anticipation reward learning.⁷⁸⁻⁸⁰ We have found that inflammatory challenge reduces neural sensitivity to reward anticipation.¹⁰⁸ We will use a laboratory based probabilistic reward task that objectively measures participants' ability to modulate behavior as a function of reward, because this task identifies reduced reward learning in depressed patients which is state-dependent and also predicts the persistent diagnosis of depression in the midst of treatment.⁷⁸⁻⁸⁰ This computerized reward-learning task is extensively described in Pizzagalli et al.¹⁰⁹

Order and Timing of Experimental Tasks: The order of the tasks will be first a randomized sequence of Reward Learning and Emotional Face Recognition, then followed by a randomized sequence of Positive Social Feedback and Cyberball Social Exclusion. Because the latter two tasks involve deception, they will be completed only once after the former two tasks, at T₂, time of peak cytokine responses. The former two tasks will be completed at T₀ and T₂.

C.2.7. Interpretation of Results and Potential Pitfalls

As leucine may not inhibit endotoxin-induced inflammation, unopposed sickness symptoms could mask the antidepressant effects of leucine assessed using the POMS. Thus, the results will be statistically adjusted for sickness symptoms. Furthermore, we will use experimental tasks of negative and positive affect to assess mood-specific processes. Although the proposed leucine dose is above average,^{30,87} the adequate antidepressant dose is unknown. Thus, if an interim data analysis for the first 30 participants using 12 g/day shows no signal of an antidepressant effect, we will consider increasing the dose to 16 g/day for the same period of 14 days. Of note, 16 g/day was the maximum dose of leucine used in long-term supplementation studies according to a meta-analysis.³⁰

C.2.8. Statistical Analysis

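### C.2.7 adjusts the results for sickness symptoms, measured after randomised pretreatment, C.2.8 has no such covariate, and nothing says which analysis is primary

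*Combined protocol and SAP*

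**What the plan says.** C.2.7 (Interpretation of Results and Potential Pitfalls) reasons that, because leucine may leave endotoxin-induced inflammation untouched, "unopposed sickness symptoms could mask the antidepressant effects of leucine assessed using the POMS". It concludes: "Thus, the results will be statistically adjusted for sickness symptoms". The sentence names no outcome, sickness score, time point or analysis tier.

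C.2.8 (Statistical Analysis) sets out a pretreatment-by-condition design analysed with linear mixed models, with time interactions for repeated measures, POMS as primary outcome, and the focus on the two endotoxin arms. Sickness does not appear in it.

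C.2.5 lists sickness among the main-session measures: "Participants will also complete self-report measures of sickness symptoms (e.g., muscle pain, fatigue". No time points are given for it. By then participants have had two weeks of randomised pretreatment, including a dose on the morning of the challenge (C.2.3).

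A.6 gives the sickness symptoms as "lethargy, fatigue, muscle pain, headache, shivering, and nausea" and states the hypothesis that leucine "will specifically abrogate depressed mood but not sickness symptoms induced by endotoxin". C.1.1 reports that leucine did not affect sickness behaviour in mice. The adverse-effect questionnaire completed at the end of pretreatment (C.2.3) shares several of these items: "symptoms include not feeling well, headache, weakness, fatigue, nausea, vomiting", with muscle pain later in the same list.

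**The concern.** Randomisation protects the comparison of POMS between leucine and placebo. It does not protect that comparison after conditioning on something measured later that the pretreatment may have changed. If leucine raises the sickness score, for instance through tolerability complaints that are also sickness items, adjustment adds an apparent mood benefit. If leucine lowers sickness, adjustment removes part of a real benefit.

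The reason given for adjusting does not require it. If leucine leaves sickness alone, sickness adds variation to mood in both endotoxin arms, which costs precision but does not bias a randomised contrast. If leucine does change sickness, the adjusted coefficient is a different quantity from the total effect.

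Also at stake is which result is the trial's result. Two sections point to different models for the primary outcome, so the choice could be made after the data are seen.

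**Working it through.** **Inputs from the documents.** Planned effect d = .70, 35 per endotoxin arm, stated power above 80% for a single time point (C.2.9). Alpha and sidedness are not stated; I assume two-sided 0.05.

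**Inputs that are assumptions.** The within-arm correlation r between mood and sickness, and the leucine effect a on sickness in SD units (positive = more sickness). The documents give neither for humans, so ranges are shown.

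**Step 1: the plan's own figure.** Unadjusted SE = √(2/35) = 0.239, and 0.70/0.239 = 2.93. Power is 83.4% (normal) or 82.3% (t). The stated figure is reproduced without a sickness covariate.

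**Step 2: effect of the adjustment.** Scale mood and sickness to within-arm SD 1, so the within-arm slope of mood on sickness equals r. A negative effect means less depressed mood. Then:

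- adjusted estimate = total effect − r × a
- adjusted SE = √(2/35) × √(1 − r²) × √(1 + a²/4)

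The last factor allows for the arm difference in sickness. The normal approximation below omits it; the t version includes it.

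**Step 3: total effect truly zero.**

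| r | a | Adjusted estimate | Rejection rate, normal | Rejection rate, t |
|---|---|---|---|---|
| .5 | 0 | 0 | 5% | 5% |
| .5 | +0.3 | −0.15 | 11.2% | 10.9% |
| .5 | +0.5 | −0.25 | 22.7% | 21.1% |
| .6 | +0.5 | −0.30 | 34.8% | 32.3% |

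Second row: 0.5 × 0.3 = 0.15; SE without the last factor = 0.239 × √0.75 = 0.207; 0.15/0.207 = 0.72. The shift is 0.15/0.70 = 21% of the planned effect. Changing the sign of a reverses the sign of the estimate and leaves the rejection rate the same.

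**Step 4: total effect truly −0.70, r = .5.**

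| a | Adjusted estimate | Power, t |
|---|---|---|
| −0.5 | −0.70 + 0.25 = −0.45 | 54.7% |
| −0.3 | −0.70 + 0.15 = −0.55 | 73.6% |
| 0 | −0.70 | 91.5% |
| +0.3 | −0.70 − 0.15 = −0.85 | 97.9% |
| +0.5 | −0.70 − 0.25 = −0.95 | 99.2% |

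**Check.** Simulating 20,000 trials of 35 per arm at r = .5 gave mean estimates of −0.45 (a = −0.5) and −0.95 (a = +0.5), power of 54.0% at a = −0.5 and 91.3% at a = 0, and null rejection rates of 20.5% and 21.2% at a = −0.5 and +0.5. These agree with the formulas.

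The calculation treats mood and sickness as single scores. The same mechanism operates in the repeated-measures model, but the sizes would depend on how sickness enters it.

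**The case against.** The best defence is that the statistical section does not include the adjustment. C.2.8 lists pretreatment, condition, their interaction and time, and the sickness sentence sits in a section on interpretation and pitfalls. A reader might infer from C.2.7 that the headline POMS result will be the adjusted one. The documents do not settle that: the sentence fits a primary or a supportive model. This stands, and the point is therefore conditional on how the adjusted result is used.

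Second, the direct evidence in the documents favours no leucine effect on sickness: the mouse result, the stated hypothesis, and the descriptions of leucine as having few or minimal adverse effects. With no effect, adjustment is unbiased and gains precision. The shared items are on a 22-item checklist of possible complaints, and being listed does not show that leucine causes them. All of this stands. But the mice received injections around the challenge, not two weeks of oral dosing, and the hypothesis is one the trial itself is meant to examine.

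Third, this is a mechanistic trial interested in a mood-specific effect. If sickness itself worsens mood, a null total effect with raised sickness implies a real direct effect, and rejecting is then not an error for that question. This also stands: the rejection rates above concern the total effect. A direct-effect reading, however, needs no unmeasured common causes of mood and sickness. Individual inflammatory reactivity is an obvious candidate, and the plan does not state the assumption.

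A reader might also see attenuation in the earlier endotoxin study, where the thresholds are p<0.001 before and p<0.05 after controlling for sickness. C.1.2 says the effects did not change, two thresholds do not show how far an estimate moved, and that study compared endotoxin with saline, not leucine with placebo. It is no evidence here.

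**Conclusion.** The point holds in conditional form. The plan announces adjustment for a post-randomisation variable, omits it from the model section, and does not say which analysis is primary. If the adjusted POMS result is used as the main result, it equals the total leucine effect only when leucine does not change sickness (or sickness is unrelated to mood within arms, which the plan's own masking argument does not assume).

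The size is unknown. It is zero if the plan's hypothesis is right. Under the assumed values it is 0.15 SD at r = .5 and a 0.3 SD sickness difference, and 0.30 SD at r = .6 and 0.5 SD, with null rejection rates of about 11% and 32-35%. If leucine lowers sickness by 0.5 SD, power at d = .70 and r = .5 falls to about 55%. None of these figures predicts what will happen in this trial, and the documents do not show that bias will occur.

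**What to change.** Amend C.2.8 to state that:

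- the primary POMS comparison and the key secondary comparisons are not adjusted for sickness symptoms;
- if a mood covariate is wanted for precision, it is the POMS taken at screening before pretreatment (C.2.4), not the T0 POMS, which already follows two weeks of randomised pretreatment;
- the sickness score, with its definition and time points, is analysed as an outcome with the same leucine-versus-placebo contrast and shown beside the mood effect, which addresses specificity directly;
- the sickness-adjusted model is a supportive, mediation-type analysis, reported with its assumption of no unmeasured confounding between sickness and mood.

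Reword C.2.7 to refer to that supportive analysis.

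The cost is wording and one extra model on data already planned, with no additional participants. If leucine truly leaves sickness unchanged, some precision is given up: at r = .5, power is about 82% instead of about 91%, still above the stated 80%. How much of that the screening POMS would recover cannot be judged from the documents. Its correlation with POMS during the session is not given, and excluding volunteers with PHQ-9 of 5 or more may narrow its spread.

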The basic design is a 2 group (leucine vs. PO placebo) by 2 condition (endotoxin vs. IV placebo) independent analysis of variance (ANOVA) with one or more repeated outcome measures analyzed with linear mixed models (LMM) with primary focus upon the two endotoxin-exposed groups. The number of repeated measures varies by assessment. The key results are the main effects of pretreatment (i.e., group) while the main effects of group, condition, and their interaction will be tested. For analyses with repeated measures, the two main effects and interaction will further interact with the time variable. POMS will be the primary outcome measure. Simes correction for multiple testing will be applied for the secondary outcome measures as they are expected to be correlated.¹¹⁰

C.2.9. Justification of Sample Size

The effect sizes for the reduction of endotoxin-induced depressive symptoms by leucine within the animal data are very large ($d=.90$), but we have assumed some attenuation in humans ($d=.70$). Assuming an effect of this size, with $n=35$ per group, there is >80% power to detect differences between the leucine and PO placebo pretreatments with endotoxin exposure for the single time point outcomes (e.g., Cyberball Social Exclusion); comparisons for repeated measures assessments will have more power (>90%) and able to detect more subtle effects at >80% power. Both 'leucine + IV placebo' and 'PO placebo + IV placebo' arms are expected to show minimal depression with means over time to be very near zero but exist as reference points to the endotoxin condition, which our previous work suggests to have large effects. With repeated measures, $n=10$ can detect

medium sized effects ($d=.50$) with power $>80\%$. Thus, there is more than adequate power with 35 vs. 10 to show the effect of endotoxin exposure within pretreatment groups.

REFERENCES

3. Depression Guideline Panel: Clinical Practice Guideline 5: Depression in Primary Care, vol 2: Treatment of Major Depression. In: US Department of Health and Human Services PHS, Agency for Health Care Policy and Research, ed. Rockville, MD. 1993.

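### The four-arm 2x2 model in C.2.8 makes no allowance for a smaller variance in the saline arms; under the usual common variance, leucine vs placebo within the endotoxin arms would be mildly anti-conservative and the interaction test would lose much of its power

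*Combined protocol and SAP*

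**What the plan says.** C.2.8 (Statistical Analysis) sets out the layout: "The basic design is a 2 group (leucine vs. PO placebo) by 2 condition (endotoxin vs. IV placebo) independent analysis of variance (ANOVA"), with linear mixed models (LMM) for repeated outcomes, "with primary focus upon the two endotoxin-exposed groups". It continues: "The key results are the main effects of pretreatment (i.e., group) while the main effects of group, condition, and their interaction will be tested". It adds: "For analyses with repeated measures, the two main effects and interaction will further interact with the time variable".

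C.2.1 gives the allocation: "n₁=35 leucine + endotoxin; n₂=35 PO placebo + endotoxin; n₃=10 leucine + IV placebo; n₄=10 PO placebo + IV placebo".

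On the two saline arms, C.2.9 (Justification of Sample Size) says that they are "expected to show minimal depression with means over time to be very near zero". Of the endotoxin condition it says "which our previous work suggests to have large effects". The power statement there is for leucine vs oral placebo under endotoxin, 35 per group.

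Neither section gives an SD for any arm, a residual or random-effect covariance structure, a degrees-of-freedom method, robust standard errors, or an alpha level.

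**The concern.** An ANOVA, or an LMM with nothing further specified, normally estimates one variance and applies it to every contrast. Here the arms are unequal in size and probably in spread. Healthy volunteers given saline, with PHQ-9 scores of 5 or more excluded, should mostly report almost no depressed mood. The endotoxin arms should respond, and not uniformly. C.2.4 reports a much stronger mood response in women, and C.1.3 a correlation between mood and IDO activity among endotoxin recipients. Both add variance in the endotoxin arms only.

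If the saline spread is smaller, a common variance is too low for a comparison of the two 35-person endotoxin arms and too high for any contrast dominated by the 10-person saline arms. Two things are then at stake: the error rate of the leucine comparison that C.2.9 powers, and the power of the interaction, which asks whether leucine acts specifically on the mood change that endotoxin induces.

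**Working it through.** **The plan's own figure.** For d=.70 and 35 per group, the noncentrality is .70 × √(35/2) = 2.93 on 68 df. Two-sided at .05 (assumed, since the plan states no alpha), power is .82. The stated >80% is reproduced.

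**Inputs.** Arm sizes 35/35/10/10 (C.2.1). Error df are 34+34+9+9 = 86, of which 68 come from the endotoxin arms. Endotoxin-arm SD is set to 1 and saline-arm SD to R. R is an assumption, so a range is shown.

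**Formulas.** Common variance = (68 + 18R²)/86. For a contrast with coefficients c, model SE² = common variance × Σ(c²/n), and true SE² = Σ(c² × SD²/n).

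**At R=.3.** Common variance = (68 + 18 × .09)/86 = .81.
- Leucine vs placebo within the endotoxin arms: model SE = √(.81 × 2/35) = .215; true SE = √(2/35) = .239. The ratio is .90, so the SE is 10% too small.
- Interaction: model SE = √(.81 × (2/35 + 2/10)) = .456; true SE = √(2/35 + .09 × 2/10) = .274. The ratio is 1.66, so the SE is 66% too large.
- Pretreatment main effect, equal cell weights: every coefficient is half the interaction's in size, so the ratio is again 1.66.
- Pretreatment main effect, n-weighted cells: model SE² = .81 × 2/45 = .0360; true SE² = 2 × (35 + 10 × .09)/45² = .0355. The ratio is 1.01.

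In the limit R=0 the first SE is 11% too small (√(68/86) = .889) and the interaction SE is 89% too large.

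**Simulated error rates and power** (normal data, single time point or subject mean, two-sided .05; repeat runs agree to within about .002 on the leucine error rate):

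| R | Type I, leucine vs placebo within endotoxin | Type I, interaction | Interaction power at d=.70, common variance | Same, separate variances |
|---|---|---|---|---|
| .2 | .081 | .001 | .23 | .77 |
| .3 | .078 | .0015 | .24 | .71 |
| .5 | .073 | .006 | .25 | .55 |
| .7 | .063 | .018 | .27 | .41 |
| 1 | .050 | .050 | .28 | .27 |

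Interaction power assumes that leucine acts only under endotoxin. Above R=1 the directions reverse: at R=1.25 the SE ratios are 1.06 and .88.

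**Endotoxin check at R=.3, common variance.** One 35 vs 10 comparison has power .24 at d=.50 (.71 with unequal variances), .79 at d=.80 and .96 at d=1.0. The four-arm endotoxin main effect has .63, .993 and 1.00 at the same effect sizes.

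**After the fix.** With arm-specific variances and Satterthwaite df, type I error is .048 to .051 for every contrast above at R from .1 to 1. Power for leucine vs placebo within the endotoxin arms stays at .82.

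**The case against.** Four points can be made for the plan.

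First, it never states a common variance. The word ANOVA may only name the factorial layout, and the primary outcome goes to an LMM, which can carry condition-specific variances. The words "with primary focus upon the two endotoxin-exposed groups" may already mean a two-arm fit, in which case the leucine comparison is sound. This stands. A reader might infer that the plan's standard errors are wrong; the documents support only that the structure is open and that its usual default is unsuitable here.

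Second, a reader might infer that the plan's key result is tested above 5%. That is not supported. C.2.8 calls the pretreatment main effects key. At R=.3 that test is conservative with equal cell weights (type I error about .0014) and about right with n-weighting (.049). Inflation affects only the simple effect within the endotoxin arms when it borrows a four-arm variance.

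Third, a reader might infer that the check that endotoxin worked loses most of its power. That holds for a modest effect in one 35 vs 10 comparison. It does not hold for the large effects that the plan expects.

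Fourth, R is not in the documents. They predict near-zero means, not small variances, and do not say whether zero is a scale floor or no change from baseline. This stands as a limit on the size. A floor would, however, produce such a ratio by itself: when normal scores with equal spread in all arms were cut off at zero, with saline means near zero, R came out at .30 to .48, with type I error of .074 to .077 for the leucine contrast and .001 to .005 for the interaction.

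**Conclusion.** The point holds conditionally. If one variance is fitted to all four arms and the saline spread is smaller, leucine vs placebo within the endotoxin arms runs at roughly 6 to 8% instead of 5%. The interaction test becomes very conservative, and for R of .5 or less it loses more than half of its attainable power at d=.70. At R=.7 the loss is smaller (.27 against .41), and at R=1 there is none.

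The stated >80% power rests on 35 vs 35 and is untouched. The figures assume normal data at a single time point; within-person correlation across the hourly POMS scores is not modelled.

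This is a worthwhile, inexpensive improvement to the analysis plan rather than a demonstrated error in it. The interaction is where the default costs most. The different behaviour of the simple effect and the two main-effect versions also shows that the plan should say which leucine contrast is primary.

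**What to change.** In C.2.8:

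1. Name leucine vs oral placebo within the endotoxin arms as the primary contrast, matching what C.2.9 powers.
2. Either fit it on the 70 endotoxin participants, or keep all 90 and estimate between-person and residual variances separately by IV condition, with Satterthwaite or Kenward-Roger degrees of freedom.
3. Use the condition-specific variances for the endotoxin and interaction tests, with Welch-type contrasts for single-time-point outcomes such as the Cyberball task.

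The cost is one model option and a few degrees of freedom. Power for the leucine contrast stays at .82. If the variances turn out equal, interaction power goes from about .28 to .27. A fully separate Welch test of 35 vs 10 gives up somewhat more in that case, because its saline variance rests on 9 df; pooling the two saline arms (18 df) limits this. If the saline variance is estimated at or near zero and the 90-person model fails to converge, the endotoxin-only fit should be the stated fallback for the primary contrast.

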The overarching objective of this innovative proof-of-concept trial is to test whether leucine pretreatment abrogates acute depressive responses to an inflammatory challenge (i.e., endotoxin) in humans, relative to placebo pretreatment. Endotoxin administration has been used as a novel experimental model of depression.¹⁹ We have demonstrated that low-dose endotoxin induces depressive symptoms in humans,²¹⁻²³ which correlate with activation of brain regions implicated in depression.³³⁻³⁵ Low-dose endotoxin also induces transient cognitive impairment,²⁰ a common symptom of depression that is often overlooked and associated with poor response to treatment.³⁶ Furthermore, we have found that endotoxin increases tryptophan-kynureneine conversion rate, which correlates with depressed mood (Preliminary Data).

This study hypothesizes that, compared to placebo pretreatment, leucine pretreatment will attenuate depressive responses to endotoxin. In this double-blind randomized placebo-controlled four-arm study of 90 healthy volunteers aged 18-65 years ($n_1=35$: oral [PO] leucine for 2 weeks followed by single intravenous [IV] endotoxin; $n_2=35$: PO placebo [i.e., maltodextrin] + IV endotoxin; $n_3=10$: PO leucine + IV placebo [i.e., saline]; $n_4=10$: PO placebo + IV placebo), we aim to:

1. Examine the effects of leucine vs. placebo pretreatment on endotoxin-induced depressive symptoms (primary outcome).
2. Examine the effects of leucine vs. placebo pretreatment on negative and positive affect responses to endotoxin (respectively, feelings of social rejection, negative bias in facial emotion recognition; and feelings of social acceptance, reward learning).
3. Examine the effects of leucine vs. placebo pretreatment on cognitive responses to endotoxin (verbal and non-verbal memory, executive function, attention).

Hypothesis: Compared to placebo pretreatment, leucine pretreatment for 2 weeks will attenuate endotoxin-induced depression outcomes including depressive symptoms, negative affect, and positive affect.

Impact Statement: If the hypotheses are confirmed, this proof-of-concept study will provide instrumental information in designing future clinical trials of leucine to treat or prevent inflammation-associated depression.

[figure not shown]

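### C.2.8 does not tie its key test to the endotoxin-arm contrast the trial was sized on; read as a four-arm main effect, single-time-point power is about 28% to 72%, against 82%

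*Combined protocol and SAP*

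**What the plan says.** C.2.8 describes a 2 (leucine or oral placebo) by 2 (endotoxin or IV placebo) design, analysed by linear mixed model where outcomes are repeated, "with primary focus upon the two endotoxin-exposed groups". It continues: "The key results are the main effects of pretreatment (i.e., group) while the main effects of group, condition, and their interaction will be tested". For repeated outcomes these terms also interact with time. POMS is the primary outcome; C.2.5 schedules it at T0, just before the injection, and hourly from T1 to T6.

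The hypothesis in Specific Aims is that "leucine pretreatment for 2 weeks will attenuate endotoxin-induced depression outcomes". C.2.9 assumes d=.70 and 35 per group, and says "there is >80% power to detect differences between the leucine and PO placebo pretreatments with endotoxin exposure for the single time point outcomes". For repeated outcomes it says "comparisons for repeated measures assessments will have more power (>90%) and able to detect more subtle effects at >80% power". The two saline arms, 10 each, are "expected to show minimal depression with means over time to be very near zero" and serve as reference points.

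The plan does not say whether the key term is fitted in two arms or four, or how cells are weighted. It also does not say whether T0 is an outcome row or a covariate, or whether group or group-by-time decides POMS.

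**The concern.** In a model that contains condition and the interaction, the group main effect is the average of two leucine effects, one under endotoxin and one under saline. Only the first is the hypothesis. If saline scores sit near zero, the second should be about zero, so the average understates the effect of interest. With equal cell weights, the two 10-person arms also supply half the estimate and most of its variance.

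A group main effect over T0–T6 has a second dilution: T0 precedes endotoxin, so an endotoxin-induced difference cannot yet exist there.

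The trial could therefore miss an effect of the size it was planned to find. With two candidates for the key result, the choice could also be made after the data are seen.

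**Working it through.** **Inputs from the documents.** Arms of 35, 35, 10 and 10 (C.2.1); d=.70 under endotoxin (C.2.9); saline means near zero (C.2.9); seven POMS times (C.2.5).

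**Assumptions, because the plan is silent.** Two-sided 0.05; SD 1 in every arm; leucine effect 0 under saline; no dropout; equal within-person correlation ρ between all times, from .3 to .9; constant d=.70 over T1–T6. Power is from the noncentral t, with 86 df unless stated.

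**1. The plan's own figure.** SE = √(2/35) = 0.239. Ratio = 0.70/0.239 = 2.93. Power is 82% (68 df; 83% by normal approximation). The stated >80% reproduces.

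**2. Four-arm main effect, one time point.**
- Equal cell weights: effect (0.70+0)/2 = 0.35; SE = ½√(2/35+2/10) = 0.2535; ratio 1.38; power 28%.
- Sample-size weights: effect 0.70×35/45 = 0.544; SE = √(2/45) = 0.211; ratio 2.58; power 72%.

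**3. POMS, four-arm main effect averaged over T0–T6.** The effect is multiplied by 6/7, because T0 contributes zero. The SD of a seven-value mean is √((1+6ρ)/7).

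| ρ | Equal weights | Sample-size weights |
|---|---|---|
| .3 | 46% | 93% |
| .5 | 34% | 83% |
| .7 | 27% | 72% |
| .9 | 23% | 63% |

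Example at ρ=.5, equal weights: 0.35×6/7 = 0.30; SD √(4/7) = 0.756; SE 0.2535×0.756 = 0.192; ratio 1.57; power 34%. The plan states >90% for repeated measures.

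**4. POMS, endotoxin arms only.** The effect is 0.70×6/7 = 0.60 over T0–T6 and 0.70 over T1–T6. The SD of a six-value mean is √((1+5ρ)/6).

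| ρ | T0–T6 average | T1–T6 average |
|---|---|---|
| .3 | 98% | 99% |
| .5 | 91% | 97% |
| .7 | 82% | 92% |
| .9 | 74% | 86% |

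**5. Adding T0 as covariate at ρ=.5.** The residual variance of the T1–T6 mean is (1+5×.5)/6 − .5² = 0.333, so the SD is 0.577. SE = 0.239×0.577 = 0.138; ratio 0.70/0.138 = 5.07; power over 99%.

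**6. Group-by-condition interaction, one time point.** Effect 0.70; SE √(2/35+2/10) = 0.507; ratio 1.38; power 28%. The interaction is no substitute for the endotoxin-arm contrast.

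**7. Sensitivity to the equal-SD assumption.** If the saline-arm SD is half the endotoxin-arm SD (normal approximation), the equal-weight single-time-point test has 26% with a pooled variance and 57% with separate variances. The weighted test has 81%.

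**The case against.** The strongest defence is the stated focus on the two endotoxin arms, which comes shortly before the key-results sentence. Restricted to those arms, the main effect of pretreatment is the 35 versus 35 contrast, and the >80% stands. Aim 1, C.2.9 and the deliberately small saline arms all point the same way. This defence stands as evidence of intent. It does not settle the test, because the key-results sentence puts the group effect beside condition and interaction, and neither can be estimated from the endotoxin arms alone.

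A reader might infer that the plan's decisive test simply has 28% power. The documents do not support that. The figure needs all four arms, equal cell weights, one time point and equal SDs, and the plan specifies no weighting. It contains no T0 dilution. The >80% belongs to single-time-point outcomes; the figure to compare with POMS is >90%.

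A reader might also expect a large loss from T0 by assuming a leucine effect that rises and falls over the session. The documents give no such profile. With a constant effect and ρ=.5, the loss in the endotoxin arms is modest, 91% against 97%. The gain from covariate adjustment is a separate matter and should not be credited to dropping T0.

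Two further points are fair. Time interactions are planned, so divergence after endotoxin is modelled, though it is not named as the key result. And a T1–T6 average adjusted for T0 is one valid choice; change from T0 or group-by-time are others.

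**Conclusion.** The concern holds on the four-arm reading: the test named in C.2.8 is then not the contrast in the hypothesis or the one powered in C.2.9. Against 82% for the powered contrast, single-time-point power falls to between 28% and 72%, depending on a weighting that the plan leaves open. For POMS with T0 averaged in, most of the weighted range and all of the unweighted range fall below the stated >90%.

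On the two-arm reading the test is the intended one. What remains is the handling of T0: averaging over T0–T6 gives about 74–98%, and T1–T6 does better at every correlation tried.

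The sizes rest on the assumptions listed above, chiefly no leucine effect under saline, equal SDs and a constant effect after endotoxin. The mismatch between the two sections does not depend on them. Because it concerns the primary outcome, it should be settled before unblinding.

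**What to change.** Replace the key-results sentence in C.2.8 with:

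> The primary test is the leucine minus PO-placebo contrast within the endotoxin condition in POMS depressed mood, averaged over T1–T6, from the LMM with T0 POMS as covariate (two-sided 0.05). Group, condition and interaction effects over all four arms are secondary.

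Report the leucine–placebo difference at T0 separately.

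The cost is SAP wording only; sample size, visits and assessments do not change. The one downside is that any leucine effect on mood already present at T0 is removed from the primary contrast. That suits the aim, which is the response to endotoxin, and the separate T0 report keeps it visible. Using T0 as a covariate is a cheap improvement on either reading of the current text.
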